11.13.15 ICH Listings

ICH : Listings					
No.	Population	IDSL / TST ID / Example Shell	Title	Programming Notes	Deliverable [Priority]
Subject Disposition					
1.	Screened	ES7	Listing of Reasons for Screen Failure	Journal Guidelines Only include failures	FSP: SAC 1
2.	Enrolled	ES2	Listing of Reasons for Study Withdrawal	ICH E3	IA 1, HR 1, SAC 1
3.	All Subjects	BL1	Listing of Subjects for Whom the Treatment Blind was Broken	ICH E3	IA 1, HR 1, SAC 1
4.	All Subjects	TA1 / CP_RD1x	Listing of Planned and Actual Treatments	IDSL Also include Allergen Strata as an additional column	IA 1, HR 1, SAC 1
Protocol Deviations					
5.	All Subjects	DV2	Listing of Important Protocol Deviations	ICH E3	IA 1, HR 1, SAC 1
6.	All Subjects	IE3	Listing of Subjects with Inclusion/Exclusion Criteria Deviations	ICH E3	IA 1, HR 1, SAC 1
Populations Analysed					
7.	Enrolled	SP3	Listing of Subjects Excluded from All Subjects, mITT, PP, PK, Sputum Populations	ICH E3 Include subjects who are randomised. If 'Enrolled' and 'All Subjects' Populations are the same, use population 'All Subjects' label and change title to 'Listing of Subjects Excluded from mITT, PP, PK, Sputum Populations.'	IA 1, HR 1, SAC 1

CONFIDENTIAL

205540

ICH : Listings					
No.	Population	IDSL / TST ID / Example Shell	Title	Programming Notes	Deliverable [Priority]
Demographic and Baseline Characteristics					
8.	All Subjects	DM2	Listing of Demographic Characteristics	ICH E3	IA 1, HR 1, SAC 1
9.	All Subjects	DM9	Listing of Race	ICH E3	IA 1, HR 1, SAC 1
Medical Conditions and Prior and Concomitant Medications					
10.	All Subjects	MH2	Listing of Past and Current Medical History		FSP: SAC 2
11.	All Subjects	CP_CM3	Listing of Concomitant Medications	IDSL	FSP: SAC 2
Exposure and Treatment Compliance					
12.	All Subjects	EX3	Listing of Exposure Data	ICH E3 GSK may have coded AR Exposure dataset to support IA	FSP: SAC 2
Adverse Events					
13.	All Subjects	CP_AE8 (Also see GSK2245035 TL7116958 idsfinal Listing 111)	Listing of All Adverse Events	ICH E3 Add columns for the CRS Category and CRS Grading	FSP: SAC 1
14.	All Subjects	AE7	Listing of Subject Numbers for Individual Adverse Events	ICH E3	FSP: SAC 1
15.	All Subjects	AE2	Listing of Relationship Between Adverse Event System Organ Classes, Preferred Terms, and Verbatim Text	IDSL	FSP: SAC 1

ICH : Listings					
No.	Population	IDSL / TST ID / Example Shell	Title	Programming Notes	Deliverable [Priority]
Cytokine Release Syndrome (CRS) Events					
16.	All Subjects	CP_AE8 (Also see GSK2245035 TL7116958 idsfinal Listing 113)	Listing of Cytokine Release Syndrome Events	List all CRS events (even ones that map to the same CRS category but a lower grade)	SAC 1
17.	All Subjects	SAFE_L2 (Also see GSK2245035 TL7116958 idsfinal Listing 115)	Listing of worst case Cytokine Release Syndrome (CRS) Score by subject and dosing visit	Also add the allergen stratum to the Treatment when setting the page by line. Handle subjects who withdraw early like Subject PP in the example shell	SAC 1
18.	All Subjects	AE7 (Also see GSK2245035 TL7116958 idsfinal Listing 114)	Listing of Subject Numbers for Individual Cytokine Release Syndrome Events	ICH E3	SAC 1
19.	All Subjects	AE2	Listing of Relationship Between Cytokine Release Syndrome Event and associated AE System Organ Classes, Preferred Terms, and Verbatim Text	IDSL	SAC 1
Serious and Other Significant Adverse Events					
20.	All Subjects	CP_AE8a	Listing of Serious Adverse Events	ICH E3	FSP: SAC 1
21.	All Subjects	SAE Reasons	Listing of Reasons for Considering as a Serious Adverse Event	FDA Note: IDSL shell in development.	FSP: SAC 1

ICH : Listings					
No.	Population	IDSL / TST ID / Example Shell	Title	Programming Notes	Deliverable [Priority]
22.	All Subjects	CP_AE8	Listing of Adverse Events Leading to Withdrawal from Study / Permanent Discontinuation of Study Treatment	ICH E3	FSP: SAC 1
Hepatobiliary (Liver)					
23.	All Subjects	MH2	Listing of Medical Conditions for Subjects with Liver Stopping Events	IDSL	FSP: SAC 2
24.	All Subjects	SU2	Listing of Substance Use for Subjects with Liver Stopping Events	IDSL	FSP: SAC 2
Laboratory – Haematology					
25.	All Subjects	LB5	Listing of All Haematology Laboratory Data for Subjects with Values of Potential Clinical Importance	ICH E3	FSP: SAC 2
26.	All Subjects	CP_LB5	Listing of Haematology Laboratory Data Values of Potential Clinical Importance		FSP: SAC 2
Laboratory – Chemistry					
27.	All Subjects	LB5	Listing of All Chemistry Laboratory Data for Subjects with Values of Potential Clinical Importance	ICH E3	FSP: SAC 2
28.	All Subjects	CP_LB5	Listing of Chemistry Laboratory Data Values of Potential Clinical Importance		FSP: SAC 2
Laboratory – Urinalysis					
29.	All Subjects	UR2a	Listing of All Urinalysis Laboratory Data for Subjects with Abnormal Values of Potential Clinical Concern	ICH E3 Abnormal values are any Positive dipstick result and/or greater than or equal to 1+ in the urine blood test and/or greater than equal to 1+ in the urine protein test	FSP: SAC 2
30.	All Subjects	UR2a	Listing of Urinalysis Laboratory Data Abnormal Values	Only include abnormal values (see above)	FSP: SAC 2

CONFIDENTIAL

205540

ICH : Listings					
No.	Population	IDSL / TST ID / Example Shell	Title	Programming Notes	Deliverable [Priority]
All Laboratory					
31.	All Subjects	LB13	Listing of Laboratory Tests and Associated Reference Ranges	Split into separate listings by chemistry, hematology, urinalysis, etc.	FSP: SAC 2
ECG					
32.	All Subjects	CP_EG3	Listing of ECG Values for Subjects with Values of Potential Clinical Importance	IDSL	FSP: SAC 2
33.	All Subjects	CP_EG3	Listing of ECG Values of Potential Clinical Importance	IDSL	FSP: SAC 2
34.	All Subjects	CP_EG5	Listing of Abnormal ECG Findings	IDSL	FSP: SAC 2
Vital Signs					
35.	All Subjects	CP_VS4	Listing of Vital Signs for Subjects with Values of Potential Clinical Importance	IDSL	FSP: SAC 2
36.	All Subjects	CP_LB5	Listing of Vital Sign Values of Potential Clinical Importance	IDSL	FSP: SAC 2

11.13.16 Non-ICH Listings

Non-ICH : Listings					
No.	Population	IDSL / TST ID / Example Shell	Title	Programming Notes	Deliverable [Priority]
Study Population					
37.	All Subjects	See GW685968_G W642444 HZA113126 final Listing 4	Listing of Skin Prick Test at Screening	Modify Example Shell Columns for Parallel group design	FSP: SAC 2
38.	All Subjects	PFT10	Listing of FEV1 and Percent Predicted FEV1 Data at Screening	Modify Shell for Parallel group design Include columns for site Footnote [1] Values have been recalculated from raw data using equations in Quanjer , 2012	FSP: SAC 2
Allergen Challenge					
39.	All Subjects	See GW685968_G W642444 HZA113126 final Listing 6	Listing of Allergen Challenge FEV ₁	Modify Example Shell Columns for Parallel group design	IA 1, HR 1, SAC 1
LAR/EAR					
40.	All Subjects	EFF_L1	Listing of Subjects Treated with Placebo Who Did Not Experience a Late Asthmatic Response at Week 9 (LAR Non-Responder at FUV1)		SAC 1

Non-ICH : Listings					
No.	Population	IDSL / TST ID / Example Shell	Title	Programming Notes	Deliverable [Priority]
41.	All Subjects	See GSK2190915 LPA111834 final Listing 8	Bronchial Allergen Challenge Listing of Minimum and Weighted Mean LAR and EAR absolute Change from Saline	Modify Example Shell Columns for Parallel group design Omit the Placebo Difference column Have Absolute (L), Change (L) and Change (%) columns for each Derived endpoint (Min and WM) Make "Treatment" the leftmost column. Period column becomes Visit.	IA 1, HR 1, SAC 1
42.	PP	n/a	Raw SAS Output for the Statistical Analysis - Bronchial Allergen Challenge Primary Analysis Minimum LAR Absolute Change from Saline at Week 9 (FUV1)		IA 1, HR 1, SAC 1
43.	PP	n/a	Raw SAS Output for the Statistical Analysis - Bronchial Allergen Challenge Primary Analysis Weighted Mean LAR Absolute Change from Saline at Week 9 (FUV1)		IA 1, HR 1, SAC 1
44.	mlTT	n/a	Raw SAS Output for the Statistical Analysis - Bronchial Allergen Challenge Minimum LAR Absolute Change from Saline at Week 9 (FUV1)	Conditional on PP and mlTT populations differing.	IA 1, HR 1, SAC 1
45.	mlTT	n/a	Raw SAS Output for the Statistical Analysis - Bronchial Allergen Challenge Weighted Mean LAR Absolute Change from Saline at Week 9 (FUV1)	Conditional on PP and mlTT populations differing.	IA 1, HR 1, SAC 1
46.	PP	n/a	Sensitivity Analysis: Raw SAS Output for the Statistical Analysis - Bronchial Allergen Challenge Minimum LAR Absolute Change from Saline at Week 9 (FUV1) using Informative Priors	Sensitivity analysis: Display priors as footnotes / or as appropriate in the output	HR 2, SAC 2
47.	PP	n/a	Sensitivity Analysis: Raw SAS Output for the Statistical Analysis - Bronchial Allergen Challenge Weighted Mean LAR Absolute Change from Saline at Week 9 (FUV1) using Informative Priors	Sensitivity analysis: Display priors as footnotes / or as appropriate in the output	HR 2, SAC 2

CONFIDENTIAL

205540

Non-ICH : Listings					
No.	Population	IDSL / TST ID / Example Shell	Title	Programming Notes	Deliverable [Priority]
48.	PP	n/a	Sensitivity Analysis: Raw SAS Output for the Statistical Analysis - Bronchial Allergen Challenge Minimum LAR Absolute Change from Saline at Week 9 (FUV1) using Blood Eosinophil level as a covariate		SAC 2
49.	PP	n/a	Sensitivity Analysis: Raw SAS Output for the Statistical Analysis - Bronchial Allergen Challenge Weighted Mean LAR Absolute Change from Saline at Week 9 (FUV1) using Blood Eosinophil level as a covariate		SAC 2
50.	PP	n/a	Raw SAS Output for the Repeated Measures Statistical Analysis - Bronchial Allergen Challenge Minimum LAR Absolute Change from Saline		SAC 2
51.	PP	n/a	Raw SAS Output for the Repeated Measures Statistical Analysis - Bronchial Allergen Challenge Weighted Mean LAR Absolute Change from Saline		SAC 2
52.	mlITT	n/a	Raw SAS Output for the Repeated Measures Statistical Analysis - Bronchial Allergen Challenge Minimum LAR Absolute Change from Saline	Conditional on PP and mlITT populations differing.	SAC 2
53.	mlITT	n/a	Raw SAS Output for the Repeated Measures Statistical Analysis - Bronchial Allergen Challenge Weighted Mean LAR Absolute Change from Saline	Conditional on PP and mlITT populations differing.	SAC 2
54.	PP	n/a	Sensitivity Analysis: Raw SAS Output for the Repeated Measures Statistical Analysis - Bronchial Allergen Challenge Minimum LAR Absolute Change from Saline using Blood Eosinophil level as a covariate		SAC 2

CONFIDENTIAL

205540

Non-ICH : Listings					
No.	Population	IDSL / TST ID / Example Shell	Title	Programming Notes	Deliverable [Priority]
55.	PP	n/a	Sensitivity Analysis: Raw SAS Output for the Repeated Measures Statistical Analysis - Bronchial Allergen Challenge Weighted Mean LAR Absolute Change from Saline using Blood Eosinophil level as a covariate		SAC 2
56.	PP	n/a	Raw SAS Output for the Statistical Analysis - Bronchial Allergen Challenge Minimum EAR Absolute Change from Saline at Week 9 (FUV1)		SAC 1
57.	PP	n/a	Raw SAS Output for the Statistical Analysis - Bronchial Allergen Challenge Weighted Mean EAR Absolute Change from Saline at Week 9 (FUV1)		SAC 1
58.	PP	n/a	Sensitivity Analysis: Raw SAS Output for the Statistical Analysis - Bronchial Allergen Challenge Minimum EAR Absolute Change from Saline at Week 9 (FUV1) using Blood Eosinophil level as a covariate		SAC 2
59.	PP	n/a	Sensitivity Analysis: Raw SAS Output for the Statistical Analysis - Bronchial Allergen Challenge Weighted Mean EAR Absolute Change from Saline at Week 9 (FUV1) using Blood Eosinophil level as a covariate		SAC 2
60.	PP	n/a	Raw SAS Output for the Repeated Measures Statistical Analysis - Bronchial Allergen Challenge Minimum EAR Absolute Change from Saline		SAC 2
61.	PP	n/a	Raw SAS Output for the Repeated Measures Statistical Analysis - Bronchial Allergen Challenge Weighted Mean EAR Absolute Change from Saline		SAC 2

Non-ICH : Listings					
No.	Population	IDSL / TST ID / Example Shell	Title	Programming Notes	Deliverable [Priority]
62.	PP	n/a	Sensitivity Analysis: Raw SAS Output for the Repeated Measures Statistical Analysis - Bronchial Allergen Challenge Minimum EAR Absolute Change from Saline using Blood Eosinophil level as a covariate		SAC 2
63.	PP	n/a	Sensitivity Analysis: Raw SAS Output for the Repeated Measures Statistical Analysis - Bronchial Allergen Challenge Weighted Mean EAR Absolute Change from Saline using Blood Eosinophil level as a covariate		SAC 2
Other Safety Parameters					
64.	All Subjects	CP_CM3	Listing of Rescue Medication (excluding that given as part of BAC procedures)	Rescue medications include Salbutamol (review with medical monitor prior to DBF the conmeds and/or any diary card data to determine if any other rescue medications exist)	FSP: SAC 2
65.	All Subjects	n/a	Listing of Disease Related Events	By Subject listing of the information collected and the derived time since 1 st dose and time since most recent dose	FSP: SAC 2
66.	All Subjects	SAFE_L3	Listing of Peak Expiratory Flow (PEF)	Also display the Max and WM summary measure. Study day does not reset when it gets to a new week.	FSP: SAC 2
67.	All Subjects	SAFE_L1	Listing of Nasal Examination Data	Use “-“ when the item was normal / not present. Wrap free text from Signs of bleeding field. Slot in any unscheduled data using the date/time of observations.	FSP: SAC 2
Pharmacokinetic					
68.	PK	pkcl1p	Listing of GSK2245035 Plasma Concentration-time Data		SAC [3]

Non-ICH : Listings					
No.	Population	IDSL / TST ID / Example Shell	Title	Programming Notes	Deliverable [Priority]
Pharmacodynamic and Biomarker					
Biomarkers supporting the BAC related exploratory objective(s)					
69.	Sputum Producers	PD_L1	Sputum Cell Pellet: Listing of evaluable data by Subject	For a sample to be evaluable it must have been both sent and viable (read without any quality issues) Order to display individuals (within each treatment): Complete profiles at top of list, then subjects with Pre-BAC SV timepoint missing, then 24h Post-BAC SV timepoint missing and finish by displaying remaining subjects by the (ascending) number of missing timepoints. In the event of identical profiles order by Allergen Strata and then subject ID.	SAC [2]
70.	Sputum Producers	PD_L2	Sputum Cell Pellet: Listing of Collection information	CONDITIONAL: Content may need revising when the precise nature of the sputum data transfer is agreed. The intent of this display is to provide the eCRF data, and whether sample sent for processing and whether it was subsequently rejected (non-viable)	SAC [2]
71.	Sputum Producers	PD_L3	Sputum Cell Pellet: Listing of Absolute Counts from each Slide Reader provided by the Vendor	CONDITIONAL: Content may need revising when the precise nature of the sputum data transfer is agreed. The intent of this display is to show the vendor provided "raw data". It may not be required	SAC [2]

Non-ICH : Listings					
No.	Population	IDSL / TST ID / Example Shell	Title	Programming Notes	Deliverable [Priority]
72.	Sputum Producers	PD_L4	Sputum Cell Pellet: Listing of Sputum Percentage data	CONDITIONAL: Content may need revising when the precise nature of the sputum data transfer is agreed. The intent of this display is to provide the raw data used in subsequent stats analyses	SAC [2]
73.	Sputum Producers	PD_L5	Sputum Cell Pellet: Listing of Absolute Cell Counts/g sputum data	CONDITIONAL: Content may need revising when the precise nature of the sputum data transfer is agreed. The intent of this display is to provide the raw data used in subsequent stats analyses	SAC [2]
74.	Sputum Producers	n/a	Sputum Cell Pellet: Raw SAS Output for the Statistical Analysis of Absolute Cell Count Pre-BAC Samples	Conditional on sufficient evaluable data points.	SAC [2]
75.	Sputum Producers	n/a	Sputum Cell Pellet: Raw SAS Output for the Statistical Analysis of all Absolute Cell Count Samples	Conditional on sufficient evaluable data points.	SAC [2]
76.	Sputum Producers	n/a	Sputum Cell Pellet: Raw SAS Output for the Statistical Analysis of Percentage Cell Counts Pre-BAC Samples	Conditional on sufficient evaluable data points.	SAC [2]
77.	Sputum Producers	n/a	Sputum Cell Pellet: Raw SAS Output for the Statistical Analysis of all Percentage Cell Counts Samples	Conditional on sufficient evaluable data points.	SAC [2]
78.	All Subjects	PD_L6	PBS Wash: Listing of concentration data		SAC [2]
79.	All Subjects	n/a	PBS Wash: Raw SAS Output for the Statistical Analysis of Pre-BAC Samples	Separate analysis for each inflammatory mediator	SAC [2]
80.	All Subjects	n/a	PBS Wash: Raw SAS Output for the Statistical Analysis of all Samples	Separate analysis for each inflammatory mediator	SAC [2]
81.	All Subjects	PD_L6	Blood Differentials: Listing of Absolute count data		SAC [2]
82.	All Subjects	PD_L6	Blood Differentials: Listing of Percentages data		SAC [2]

CONFIDENTIAL

205540

Non-ICH : Listings					
No.	Population	IDSL / TST ID / Example Shell	Title	Programming Notes	Deliverable [Priority]
83.	All Subjects	n/a	Blood Differentials: Raw SAS Output for the Statistical Analysis of Absolute Count Pre-BAC Samples		SAC [2]
84.	All Subjects	n/a	Blood Differentials: Raw SAS Output for the Statistical Analysis of all Absolute Count Samples		SAC [2]
85.	All Subjects	n/a	Blood Differentials: Raw SAS Output for the Statistical Analysis of Percentages Pre-BAC Samples		SAC [2]
86.	All Subjects	n/a	Blood Differentials: Raw SAS Output for the Statistical Analysis of all Percentages Samples		SAC [2]
87.	All Subjects	PD_L7	FeNO: Listing of All FeNO data	Include BAC and Dosing Visit samples in the same listing.	SAC [2]
88.	All Subjects	n/a	FeNO: Raw SAS Output for the Statistical Analysis of BAC Visit FeNO data		SAC [2]
Biomarkers supporting the NAC related exploratory objective(s)					
89.	All Subjects	PD_L8	Nasal Lavage: Listing of Fluid and Filter Concentration data (All NAC associated Timepoints)	Include all data from all NAC visit planned timepoints in this listing (i.e. Background, Pre-NAC, 5m Post NAC and 6h Post NAC for SV, FUV1, FUV2)	SAC [2]
90.	All Subjects	n/a	Nasal Lavage: Raw SAS Output for the Statistical Analysis of NAC Background Samples	Separate analysis for each biomarker (Fluid and Filters)	SAC [2]
91.	All Subjects	n/a	Nasal Lavage: Raw SAS Output for the Statistical Analysis of Direct NAC Samples	Separate analysis for each biomarker (Fluid and Filters)	SAC [2]
Biomarkers supporting the Induction of TLR7 (target engagement) exploratory objective(s)					
92.	All Subjects	PD_L8	Nasal Lavage: Listing of Fluid and Filter Concentration data (All Dosing Visit associated Timepoints)	Include all data from all Dosing Visit planned timepoints in this listing (i.e. Pre-Dose and 24h Post Dose for DV1, DV4 and DV8)	SAC [2]

Non-ICH : Listings					
No.	Population	IDSL / TST ID / Example Shell	Title	Programming Notes	Deliverable [Priority]
93.	All Subjects	n/a	Nasal Lavage: Raw SAS Output for the Statistical Analysis of Dosing Visit Samples	Separate analysis for each biomarker	SAC [2]
94.	All Subjects	PD_L8	Serum: Listing of Concentration data	Drop the volume of sample column.	SAC [2]
95.	All Subjects	n/a	Serum: Raw SAS Output for the Statistical Analysis of Dosing Visit Samples	Separate analysis for each biomarker	SAC [2]
96.	All Subjects	n/a	FeNO: Raw SAS Output for the Statistical Analysis of Dosing Visit FeNO data		SAC [2]
Multivariate / Composite					
97.	All Subjects	n/a	Multivariable responder/non-responders: Listing of Question IDs and their associated text / criteria	Note: Data may drive the addition or removal of questions/criteria. Any new post hoc additions (but not counting re-ordering of items in Table 15) should be indicated using a lowercase p as a suffix, e.g. N1p, N2p	SAC [2]
98.	All Subjects	n/a	Multivariable responder/non-responders: Listing of Individual subjects responder status to each Question ID	To Save space use the abbreviated question IDs (e.g. A1, B1, N1p etc) and add footnote referring the reader to the Output with the link to the full text/criteria (i.e. the listing number that is used at time of reporting) Note: Individual questions may use different analysis populations and the All Subjects has been specified here because it should encompass all of them.	SAC [2]

CONFIDENTIAL

205540

Non-ICH : Listings					
No.	Population	IDSL / TST ID / Example Shell	Title	Programming Notes	Deliverable [Priority]
99.	All Subjects	n/a	Multivariable responder/non-responders: Listing of the Proportion of responders for each Question ID by Treatment	To Save space use the abbreviated question IDs (e.g. A1, B1, N1p etc) and add footnote referring the reader to the Output with the link to the full text/criteria (i.e. the listing number that is used at time of reporting) Derive separate proportions for the main and alternate sets of treatment descriptors.	SAC [2]
100.	All Subjects	n/a	Multivariate Approach 1 - Profile Regression Raw Output		SAC [2]
101.	All Subjects	n/a	Multivariate Approach 2 – Raw Output		SAC [2]
Exploratory					
102.	All Subjects	Base around principles of gsk2245035 mid204540 final listing 13	Listing of Total Nasal Symptom Score (TNSS)	Include individual components and total. Include column for the overall daily score (akin to the BAC FEV1 repeat measures from a timepoint being modelled using their max value)	FSP: SAC [2]
103.	All Subjects	Base around principles of gsk2245035 mid204540 final listing 14 & 15	Listing of Weighted Mean Total Nasal Symptom Score (TNSS)	Include WMs derived for individual components and total for each study week	FSP: SAC [2]
104.	All Subjects	EXP_L1	Listing of Intradermal Allergy Testing – Wheal/Flare data	List Negative control and Challenge (Allergen) data on same row if possible.	FSP: SAC [2]

Non-ICH : Listings					
No.	Population	IDSL / TST ID / Example Shell	Title	Programming Notes	Deliverable [Priority]
105.	All Subjects	EXP_L2	Listing of Intradermal Allergy Testing – Change from Baseline Mean Diameter Wheal/Flare data	List Negative control and Challenge (Allergen) data on same row if possible. Include SV2 absolute value (baseline) as a row and then the change from baselines as record per visit underneath	FSP: SAC [2]
Interim Analysis Specific					
106.	All Subjects (at the time of IA1)	EFF_L1	Interim Analysis: Listing of Subjects Treated with Placebo Who Did Not Experience a Late Asthmatic Response at Week 9 (LAR Non-Responder at FUV1)	1 st Section: Table of how many non-LAR responders there were on Placebo at FUV1 2 nd Section: Lists the non-LAR responders (if any) and which item(s) they failed on	IA [1]
107.	All Subjects (at the time of IA1)	EFF_L2	Interim Analysis: Raw SAS output from predicting the probability of achieving end of study success	Conditional on observed data at time of interim (Consult GSK Study statistician to determine whether to produce)	IA [1]

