### 7.1.3. Time and Events Table – Follow up visits (FUV1 to 3) (Weeks 9 to 20)

Procedure	Follow up Visit 1 (FUV1)		Follow-up Visit 2 (FUV2)			2 month follow-up phone call (Week 16)	Follow up Visit 3 (FUV3)			Notes	
	Week 9 (1 week after DV8)	24 hours later	Week 11 (3 weeks after DV8)	Week 12 (4 weeks after DV8)	24 hours later		Week 19 (11 weeks after DV8)	Week 20 (12 weeks after DV8)	24 hours later		
AE/SAE review	<=====>			X 	<=====>						
Concomitant medication review	<=====>			X 	<=====>					 Phone call made to the subject to check AEs and concomitant medications and confirm availability for FUV3	
Diarycard collection, review and dispensing	X									Review diary card at every visit until the end of FUV 2	
FeNO measurement	X	X		X	X			X	X	Collect prior to sputum induction	
Blood sample for RNA analysis				X						PAX tubes for /AFFY chip gene expression in blood. Collected prior to the bronchial allergen challenge at FUV2	
Saline and bolus BAC challenge plus associated spirometry measurements	X			X				X		Including pre-procedure FEV 1 assessment and repeat FEV 1 measurements up to 10 hours post BAC	
Sputum induction and processing for BAC associated sample collection		X	X		X		X		X	Sputum induction pre-BAC and 24 hours after BAC	
Laboratory assessments (haematology only)	X	X		X	X		X 	X		Blood samples should be taken pre-BAC and on the following day at 24hrs post BAC	
Blood samples for PBMC preparations	X			X				X		Blood samples for PBMC preparations (pre-BAC and 6 hours after BAC)	

Procedure	Follow up Visit 1 (FUV1)		Follow-up Visit 2 (FUV2)			2 month follow-up phone call (Week 16)	Follow up Visit 3 (FUV3)			Notes
	Week 9 (1 week after DV8)	24 hours later	Week 11 (3 weeks after DV8)	Week 12 (4 weeks after DV8)	24 hours later		Week 19 (11 weeks after DV8)	Week 20 (12 weeks after DV8)	24 hours later	
Nasal lavage		X			X					Collect nasal lavage to provide a background sample. Repeat nasal lavage pre-NAC, then again 5 minutes and at least 6 hours post-NAC.
Nasal filter collection		X			X					Collect nasal filter sample to provide a background pre-wash sample, after nasal wash repeat nasal filter sampling pre-NAC, then again 5 minutes and at least 6 hours post-NA.
NAC		X			X					Commence after the 24-hour BAC sputum and blood biomarker samples have been taken at FUV1 and FUV2

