#### **7.4.1.5. Disease-Related Events and/or Disease-Related Outcomes Not Qualifying as SAEs**

The following disease related events (DREs) are common in subjects with mild allergic asthma and can be serious/life threatening:

- Wheeziness
- Chest tightness or chest heaviness
- Coughing

Because these events are typically associated with the disease under study, they will not be reported according to the standard process for expedited reporting of SAEs to GSK (even though the event may meet the definition of a SAE). These events will be recorded on the DRE page in the subject's CRF within 5 working days.

*NOTE: However, if either of the following conditions apply, then the event must be recorded and reported as an SAE (instead of a DRE):*

- *The event is, in the investigator's opinion, of greater intensity, frequency, or duration than expected for the individual subject, or*
- *The investigator considers that there is a reasonable possibility that the event was related to treatment with the investigational product.*

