#### Events meeting AE definition include:

- Any abnormal laboratory test results (hematology, clinical chemistry, or urinalysis) or other safety assessments (e.g., ECGs, radiological scans, vital signs measurements), including those that worsen from baseline, and felt to be clinically significant in the medical and scientific judgement of the investigator.
- Exacerbation of a chronic or intermittent pre-existing condition including either an increase in frequency and/or intensity of the condition.
- New conditions detected or diagnosed after study treatment administration even though it may have been present prior to the start of the study.
- Signs, symptoms, or the clinical sequelae of a suspected interaction.
- Signs, symptoms, or the clinical sequelae of a suspected overdose of either study treatment or a concomitant medication (overdose per se will not be reported as an AE/SAE unless this is an intentional overdose taken with possible suicidal/self-harming intent. This should be reported regardless of sequelae).
- "Lack of efficacy" or "failure of expected pharmacological action" per se will not be reported as an AE or SAE. However, the signs and symptoms and/or clinical sequelae resulting from lack of efficacy will be reported if they fulfil the definition of an AE or SAE.

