**Events NOT meeting definition of an AE include:**

- Any clinically significant abnormal laboratory findings or other abnormal safety assessments which are associated with the underlying disease, unless judged by the investigator to be more severe than expected for the subject's condition.
- The disease/disorder being studied or expected progression, signs, or symptoms of the disease/disorder being studied, unless more severe than expected for the subject's condition.
- Medical or surgical procedure (e.g., endoscopy, appendectomy): the condition that leads to the procedure is an AE.
- Situations where an untoward medical occurrence did not occur (social and/or convenience admission to a hospital).
- Anticipated day-to-day fluctuations of pre-existing disease(s) or condition(s) present or detected at the start of the study that do not worsen.

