### 12.4.3. Definition of Serious Adverse Events

If an event is not an AE per definition above, then it cannot be an SAE even if serious conditions are met (e.g., hospitalization for signs/symptoms of the disease under study, death due to progression of disease, etc).

Serious Adverse Event (SAE) is defined as any untoward medical occurrence that, at any dose:
a. Results in death
b. Is life-threatening
NOTE:
The term 'life-threatening' in the definition of 'serious' refers to an event in which the subject was at risk of death at the time of the event. It does not refer to an event, which hypothetically might have caused death, if it were more severe.
c. Requires hospitalization or prolongation of existing hospitalization
NOTE:

 
In general, hospitalization signifies that the subject has been detained (usually involving at least an overnight stay) at the hospital or emergency ward for observation and/or treatment that would not have been appropriate in the physician's
 

office or out-patient setting. Complications that occur during hospitalization are AEs. If a complication prolongs hospitalization or fulfills any other serious criteria, the event is serious. When in doubt as to whether "hospitalization" occurred or was necessary, the AE should be considered serious.
 

• Hospitalization for elective treatment of a pre-existing condition that did not worsen from baseline is not considered an AE.

d. Results in disability/incapacity
 
NOTE:
 

• The term disability means a substantial disruption of a person's ability to conduct normal life functions.

• This definition is not intended to include experiences of relatively minor medical significance such as uncomplicated headache, nausea, vomiting, diarrhea, influenza, and accidental trauma (e.g. sprained ankle) which may interfere or prevent everyday life functions but do not constitute a substantial disruption

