11.3.2.1 Treatment States for AE (and DRE) Data

Treatment State	Definition
Pre-Treatment	AE Start Date/Time < Study Treatment Start Date/Time
On-Treatment*	If AE onset date/time is on or after treatment start date/time & on or before treatment stop date/time. Study Treatment Start Date/Time ≤ AE Start Date/Time ≤ Study Treatment Stop Date/Time + 7
Post-Treatment*	If AE onset date is after the treatment stop date. AE Start Date > Study Treatment Stop Date + 7
Onset Time Since 1 st Dose (Days)	If Treatment Start Date > AE Onset Date = AE Onset Date – Treatment Start Date If Treatment Start Date ≤ AE Onset Date = AE Onset Date – Treatment Start Date + 1 Missing otherwise.
Duration (Days)	AE Resolution Date – AE Onset Date + 1
Drug-related ^Δ	If relationship is marked 'YES' on eCRF OR value is missing

NOTES:

- * Treatment phase assumes that the effects of study treatment duration will last a week.
- Study Treatment Start relates to the 1st dose received by the individual and the Study Treatment Stop relates to the final dose received by the individual. If the study treatment stop date is missing then the AE will be considered to be On-Treatment.
- Δ=Not applicable/required for DRE

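### Disease-related events (wheeze, chest tightness or heaviness, cough) are planned only as a by-subject listing, so no planned output compares them between arms

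*SAP*

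**What the plan says.** Protocol Section 7.4.1.5 names three kinds of symptom as DREs: wheeze, chest tightness or heaviness, and cough. It takes them out of expedited SAE reporting, "even though the event may meet the definition of a SAE", and has them entered on a DRE page of the CRF. Two conditions return an event to SAE reporting: it is, in the investigator's opinion, "of greater intensity, frequency, or duration than expected for the individual subject", or there is a reasonable possibility that the investigational product caused it.

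Protocol Section 12.4.1 bears on the same events from both sides. A worsening of an existing condition, including "an increase in frequency and/or intensity of the condition", is an AE. By contrast, "expected progression, signs, or symptoms of the disease/disorder being studied" do not count as AEs unless more severe than expected. Section 12.4.3 adds that if an event is not an AE, "then it cannot be an SAE even if serious conditions are met".

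In the SAP, Table 7 (Section 8.2.1) marks DREs for a listing, with no table and no figure. Section 11.13.16 carries this out as Listing 65, All Subjects: "By Subject listing of the information collected and the derived time since" first dose and most recent dose. Section 11.5.3 derives those two intervals and nothing else for DREs. Protocol Section 9.4.3 leaves the choice between summary, graph and listing open for safety data.

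**The concern.** The trial has a safety and tolerability objective in people with asthma, and these are the symptoms of that disease. Whether an event is expected is judged one subject at a time by a blinded investigator. That judgement can pick up a subject who is clearly worse than usual. It cannot see that one arm has more subjects with symptoms that each look ordinary. Only a comparison with placebo shows that, and the plan never tabulates these events by arm.

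At stake is the completeness of the tolerability account in the study report. The primary LAR analysis is not affected.

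**Working it through.** No figure in the plan is at issue, so the check is an inventory of outputs followed by tracing where an event goes.

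**1. Inventory of planned safety outputs (SAP Sections 11.13.7, 11.13.8 and 11.13.16).**

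- Tables: AEs 3.1–3.5 (5), cytokine release events 3.6–3.7 (2), SAEs 3.8–3.9 (2), chemistry 3.10–3.11 (2), haematology 3.12–3.13 (2), liver 3.14 (1), ECG 3.15–3.16 (2), vital signs 3.17 (1), concomitant medication 3.18 (1), rescue 3.19 (1), PEF 3.20–3.21 (2), nasal examination 3.22–3.23 (2). Sum: 5+2+2+2+2+1+2+1+1+1+2+2 = 23. Naming DREs: 0.
- Figures: PEF 3.1–3.3 and cytokine release events 3.4, so 4. Naming DREs: 0.
- Listings: Listing 65 is the only one for DREs.

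**2. Could DREs enter through the AE or SAE tables?** Take a wheeze that the investigator judges expected for that subject and unrelated to drug.

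- Section 7.4.1.5 sends it to the DRE page.
- Section 12.4.1 says it is not an AE, so it should not be in Tables 3.1–3.5.
- Section 12.4.3 says that it then cannot be an SAE, so it should not be in Tables 3.8–3.9, even if it met a serious criterion.

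The SAP never states this. Table 7 places DREs in the AE overview and labels them as AEs, and Section 11.3.2.1 applies the AE treatment states to them. Against that, the same section says the drug-related flag does not apply to DREs, which in effect keeps them out of the drug-related Tables 3.2 and 3.4. The open question is therefore confined to Tables 3.1, 3.3 and 3.5, where exclusion is the more natural reading.

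**3. What leaves the DRE set.** Events worse than expected, or possibly drug-related, are reported as SAEs and so reach the AE outputs. What remains is an arm-level difference made of individually expected, apparently unrelated events.

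**4. Indirect routes to a by-arm view.**

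- Table 3.19 (rescue use) leaves out rescue given as part of the bronchial challenge.
- PEF is recorded daily from the first dosing visit only to the 4-week follow-up (Protocol Section 7.4.7).
- FEV₁ after challenge is compared by arm, but only on challenge days.
- The ongoing safety review is unblinded, but SAP Section 3.3 places it outside the SAP, so it need not appear in the report.

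**5. Resolution of a table.** With about 24 subjects per arm, one subject is 1/24 = 4.2 percentage points. The documents give no DRE rate, so an expected count cannot be derived.

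**The case against.** The strongest reply is that nothing here is wrong. The protocol permits listings. The safety endpoints it names are AEs, PEF, rescue salbutamol and laboratory parameters; DREs are not among them, and each named endpoint has output by arm. Worrying events are escalated out of the DRE set. The safety review is unblinded and involves an external expert. In a trial of about 48 subjects, anyone can tally Listing 65 by arm. Counts will be small, and symptoms on challenge days partly repeat what FEV₁ already measures.

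Much of this stands. The listing is allowed, escalation narrows the gap, and a table finely divided by symptom and period would be nearly empty, so the split should be coarse. Two parts do not stand. Rescue use and peak flow are related measures and do not count these symptoms. A hand tally by the reader is also a weaker basis than a table fixed before database freeze.

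A reader might infer that serious asthma events could disappear from the report. The documents do not support that: every DRE appears in Listing 65, and those worse than expected or possibly drug-related are reported as SAEs. A reader might also infer that the SAP leaves all five AE tables undetermined; the drug-related flag rule in effect settles 3.2 and 3.4.

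**Conclusion.** The point holds as a reporting gap: one listing, no table, no figure, and definitions that most naturally keep expected wheeze, chest tightness and cough out of the AE and SAE tables. No planned output therefore compares these events between arms. It is an improvement worth making because it is cheap and serves a stated objective.

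It should not be read as a departure from the protocol, since Section 9.4.3 allows listing. Nor should a table at this sample size be expected to establish or exclude harm; its purpose is description.

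The conclusion rests on reading the AE definition as excluding expected DREs, which the SAP's own label for them slightly contradicts, and on the numbered list of displays being complete. The mock shells are a separate document and were not available, but the list contains no DRE table for a shell to serve.

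**What to change.** Add one descriptive table by arm, All Subjects population:

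- number and percentage of subjects with at least one DRE, and number of events, overall and by symptom if the DRE page records symptom type (the page is not shown in the documents);
- two periods only: before the FUV1 challenge, and from that challenge onward. This keeps the treatment period apart from the follow-up period, in which bronchial challenges can themselves provoke these symptoms;
- one row pooling AE and DRE records of the same symptoms, so that the comparison does not depend on which page the investigator chose.

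No test or threshold is needed. As a minor clarification, add a sentence saying that DREs are not counted in Tables 3.1, 3.3 and 3.5.

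The cost is one extra table with sparse counts at about 24 per arm, and one sentence. SAP Section 11.5.3 says DRE start and stop date/times are recorded, so beyond the symptom field only challenge dates are needed. Both changes should be made before database freeze.
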